*Primary objective(s):* To determine the feasibility of performing HIVM in patients with deep space solid tumors during standard course of surgical resection. A successful intravital microscopic observation will include the ability to complete each of the following:

1. Identify and measure vessels associated with tumor
2. Determine vessel density per 10x field
3. Visualize vital dyes within the vessels (fluorescein)
4. Calculate the blood flow velocity of the vessels and tissue penetration of fluorescein as a marker of vessel permeability.
5. Obtain these vessel parameters after administration of an IV fluid bolus and/or vasopressor administration (phenylephrine or vasopressin) during the normal course of the surgical resection.

*Secondary objective(s):*

1. Compare the microscopic observation of the tumor-associated vessels with normal tissue (e.g. peritoneal surface) in each individual subject.
2. Correlate the microscopic observations of the tumor-associated vessels with pathologic grade of tumor.
3. To correlate the microscopic observation of the microvasculature with tumor-specific and overall survival.

Study Design: This is a non-randomized, single center, study of HIVM observation in subjects with deep space solid tumors undergoing surgical resection.

All subjects will meet the inclusion and exclusion criteria prior to participation in this study. Standard evaluation by the Preoperative Anesthesia clinic at Mayo Clinic Florida may include additional testing such as EKG, chest x-ray, and/or pulmonary function tests.

The study will be performed in two parts. Part 1 will enroll 10 patients with an expected feasibility rate of 70%. Whereas the feasibility rate in primary melanoma was 90%, the expected feasibility rate for deep space tumors may be lower as the site is in an anatomically deeper location. If Part 1 is not met (i.e. in three or more patients), the primary objective would not be considered technically feasible, and then the study will be stopped. If Part 1 is fulfilled, then the study will continue with an additional 40 patients enrolled (total of 50 patients). Accrual is expected to take 2.5 years.

*Inclusion criteria:*

1. Age  $\geq$  18 years of age.
2. ECOG Performance Status of  $\leq 2$ .
3. Measurable tumor by direct visualization requiring surgical resection in the OR.

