Technical difficulties with the microscope apparatus (e.g. malfunction of the software or structural damage to any of the microscope components) or unforeseen events during the course of surgery that are unrelated to the study intervention but that result in the termination of the surgery (e.g. adverse reaction to anesthetic prior to administration of fluorescein or hemodynamic instability from a complication of the surgery) will not be considered failures of the primary objective. In these circumstances, the subject will be considered to be off-study and be replaced with a subsequent patient. If vasopressors are not administered during the course of the surgery, the patient data will still be included in the study as it addresses Aim 1.

Off-line analysis of digitally recorded live video will be performed using parameters and statistical methods that have been developed in our preclinical imaging studies.[1] Lumenal cross-sectional diameter (D) of vessels and velocity (V) of dye labeled cells will be measured in off-line observations. Wall shear rate ( $\gamma$ ) will be calculated as  $8(V \div D)$ .[44] Vessel density will be determined by measuring the calculated blood vessel area as a percent of the total visual field area. If visible, the uptake of fluorescein will be measured as a diffusion rate (distance from tumor vessel over time) and as a percent of the total tumor field observed (percent of visual field expressed as surface area with dye detected). Blood flow velocity will be determined by the equation  $Q = (RBC \text{ velocity}/1.6) \times (d/2) \times \pi$ . Software is available from Mauna Kea, which can analyze and calculate these data.

These data will be calculated and recorded in a spread sheet that will also be saved onto a password-protected hard drive in the Principal Investigator's laboratory. Additionally, all data will be de-identified and provided to the Biostatistician. Generated data and the raw video images will be stored for review at any time to satisfy any audit of the collected data. This saved data will readily allow the determination of a successful observation including the identification of tumor vessels, the associated vessel measurements, vessel density, and dye enhanced imaging acquisition.

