## **9 STATISTICAL METHODOLOGY**

Initially ten patients will be treated to determine the feasibility of HIVM for deep space tumors. This first part of the study is a pilot study of feasibility. If seven or more patients are deemed a success by meeting all of the criteria below, then HIVM will be deemed feasible in the study of deep space tumors. Criteria include the ability to complete each of the following:

1. Identify and measure vessels associated with tumor
2. Determine vessel density per 10x field
3. Visualize vital dyes within the vessels (fluorescein)
4. Calculate the blood flow velocity of the vessels and tissue penetration of fluorescein as a marker of vessel permeability.

If the true success rate is 60%, the probability of deeming HIVM feasible is 63%; if the true success rate is 70%, then the probability of deeming HIVM feasible is 88%; and if the true success rate is 90%, then the probability of deeming HIVM feasible increases to 99%.

If HIVM is deemed feasible, then an additional 40 patients will be accrued to this study in order to address the following:

1. Post-operative comparison of the microvasculature of tumor with normal tissue (peritoneum) in each individual subject using vessel diameters, vessel density, detection of intravital dye and flow rates.
2. Post-operative correlation of the microvasculature with pathologic features of the tumor (i.e. tumor grade) at the time of the final pathology report (5-7 days after surgery).
3. Post-operative correlation of the microscopic observation of the tumor microvasculature tumor-specific and overall survival.

An abnormal HIVM observation is defined by any of the following criteria:

1. Aberrant vessel structure compared to normal tissue, which includes tortuosity of the vessel wall or a closed loop formation.
2. Aberrant vessel branching patterns compared to normal tissue, which includes erratic and disorganized branching points.
3. Blood vessel density that is less than or greater than one standard deviation of the blood vessel density observed in normal tissue.
4. Inability to detect flow or fluorescein within a vessel.
5. Average blood flow rate through observed vessel that is less than one standard deviation of the average blood flow rate through a normal vessel.

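### The Part 1 feasibility rate is conditional on a working microscope, and the plan does not report the all-attempt rate beside it

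*Combined protocol and SAP*

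**What the plan says.** Section 4.2 (Study Methods) names two kinds of event that "will not be considered failures of the primary objective". One is technical difficulty with the microscope apparatus, illustrated by software malfunction and structural damage to components. The other is an unforeseen surgical event, unrelated to the study intervention, that ends the operation. In either case "the subject will be considered to be off-study and be replaced with a subsequent patient". The condition that the surgery was terminated belongs to the second kind only. A microscope failure during an operation that is otherwise completed is therefore also removed and replaced.

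Section 9 opens the decision rule with "Initially ten patients will be treated to determine the feasibility of HIVM for deep space tumors" and continues: "If seven or more patients are deemed a success by meeting all of the criteria below, then HIVM will be deemed feasible". It mentions neither exclusions nor replacements, and it plans no analysis over all subjects in whom HIVM was attempted. The synopsis, under Study Design, attaches the label: if Part 1 is not met, "the primary objective would not be considered technically feasible, and then the study will be stopped".

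The documents give no microscope failure rate, no closed definition of a technical difficulty, no limit specific to replacements and no commitment to report how many subjects were replaced. The accrual section and section 9 set a maximum of 50 subjects without saying whether replaced subjects count toward it.

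**The concern.** The primary objective is whether HIVM can be performed during resection of deep space tumors. Instrument reliability in that setting is part of the answer a later user would want. Section 4.2 describes a device typically used on gastrointestinal mucosa and now applied through open, laparoscopic or robotic approaches, so damage or malfunction may arise from the very setting under test. Nothing in the plan separates that from chance breakdown.

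Because the list of difficulties is given by example, its boundary is also open. Several success criteria depend on off-line analysis of the video, for which vendor software is cited, and software malfunction is not restricted to image capture. A measurement that could not be obtained might be classed as a failure or as a replaceable technical difficulty, and the plan does not say who decides or when.

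What is at stake is the meaning of the Part 1 result. A reader told that HIVM was technically feasible in 70% of patients would not know whether ten attempts or thirteen lay behind that figure, and the same result opens enrolment of 40 more patients.

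**Working it through.** **Inputs.** Ten counted patients and a go rule of at least 7 successes (section 9). The synopsis wording conflicts with this: "If Part 1 is not met (i.e. in three or more patients), the primary objective would not be considered technically feasible". Read as three or more failures, it requires at least 8 successes to continue, so both versions are shown. The malfunction share *f* of all attempts is not in the documents; 0%, 5%, 10% and 20% are assumptions.

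**The plan's own figures.** Section 9 states a probability of declaring feasibility of 63%, 88% and 99% at true rates of 60%, 70% and 90%. The exact binomial tail P(X ≥ 7 | n = 10) gives 38.2%, 65.0% and 98.7%. Only the last agrees. A cut-off of 6 gives 63.3%, 85.0% and 99.8%; a cut-off of 8 gives 16.7%, 38.3% and 93.0%. No cut-off with ten patients reproduces all three. This is a separate matter, but it means the stated 63% cannot serve as the reference here; 38.2% is used.

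**Effect of replacement on the rate.** Let *p* be the success rate over all attempts. A malfunction is never a success, so once those attempts are removed, the ten counted patients have success rate *p*/(1 − *f*). With *p* = 60%:

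| Assumed *f* | Rate after replacement | P(≥ 7 of 10) | P(≥ 8 of 10) |
|---|---|---|---|
| 0% | 0.60/1.00 = 60.0% | 38.2% | 16.7% |
| 5% | 0.60/0.95 = 63.2% | 46.4% | 22.4% |
| 10% | 0.60/0.90 = 66.7% | 55.9% | 29.9% |
| 20% | 0.60/0.80 = 75.0% | 77.6% | 52.6% |

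If malfunctions were counted as non-success among ten attempts, the probability would stay at the 0% row whatever *f* is.

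**The same comparison from the other side.** Fix success with a working microscope at 70%. Replacement then leaves P(≥ 7 of 10) at 65.0% for every *f*. Counting malfunctions would test 0.70 × (1 − *f*), giving 55.5%, 46.0% and 28.8% at *f* = 5%, 10% and 20%.

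**What a reported 7 of 10 can hide.** With *k* replaced microscope failures the all-attempt proportion is 7/(10 + *k*):

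| *k* | Proportion of attempts | Exact (Clopper-Pearson) 95% CI |
|---|---|---|
| 0 | 7/10 = 70.0% | 35% to 93% |
| 1 | 7/11 = 63.6% | 31% to 89% |
| 2 | 7/12 = 58.3% | 28% to 85% |
| 3 | 7/13 = 53.8% | 25% to 81% |

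The expected number of replacements while accruing ten counted patients is 10*f*/(1 − *f*): about 0.5, 1.1 and 2.5 at *f* = 5%, 10% and 20%. The last row corresponds to 3/13 = 23% malfunction, just above the assumed range.

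**The case against.** The rule is open and set in advance. The synopsis explains the lower expected rate by the deeper anatomical site, so the uncertainty it describes is about access and not about instrument reliability. The endpoint asks whether vessels, density, dye and velocity can be measured, and the instrument is already in use in the sponsor's peritoneal carcinomatosis trial. Success given a working microscope is a sensible pilot quantity, and if the true rate is defined that way, replacement does not change the probability of going on. All of this stands, and it is why counting malfunctions as failures in the decision rule itself is a matter of preference.

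A reader might go further and infer three things that the documents do not support.

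- *That the rate is wrongly inflated and the go decision too easy.* The plan states no unacceptable rate and no type I error, so there is no benchmark for too easy. The upward shift is relative to an all-attempt rate that the plan never adopted as its target.
- *That the shift is known to be large.* No malfunction rate is given. At 0% nothing changes, and at 5% the probability moves from 38% to 46%.
- *That replacement is unlimited.* Enrolment has a maximum of 50. What is missing is a limit on replacements as such and a statement of whether they count toward that maximum.

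Replacing subjects whose surgery ended for reasons unrelated to HIVM is also a different case and is readily defended.

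What the objection does not answer is the label. A conclusion of technical feasibility, drawn only from procedures in which the device worked, says more than the data behind it unless the condition is stated.

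**Conclusion.** The point holds as one of definition and reporting. The Part 1 rate is conditional on a working microscope and exceeds the all-attempt rate whenever at least one microscope failure is replaced. The direction is certain; the size is unknown. If all-attempt success is 60% and malfunction is assumed at 0% to 20%, the probability of passing ranges from 38% to 78% under the section 9 rule, and from 17% to 53% under the synopsis wording. These figures rest on the assumed *f*, on a constant success rate and on independence between patients. The proportions for 7 of 10 with one to three replacements (64%, 58%, 54%) need no assumption about *f*. This is a cheap improvement that changes what the trial can conclude; it does not show that the prespecified rule is invalid.

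**What to change.** In section 9:

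1. Beside the evaluable rate, report successes over all subjects in whom HIVM was attempted after tumor exposure, counting microscope malfunction or damage as non-success, with an exact 95% confidence interval.
2. Report the number of replacements and the reason for each.
3. Describe HIVM as technically feasible without qualification only if the all-attempt proportion also reaches 70%. Stating this as a proportion avoids applying a 7-of-10 count to eleven or more attempts. Otherwise, state that feasibility is conditional on a working device.

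Two short clarifications would support this: replace the open list of technical difficulties in section 4.2 with a closed one, and say whether replaced subjects count toward the maximum of 50. Replacement of subjects whose surgery ended for reasons unrelated to HIVM may stay as written. The 7-of-10 rule in section 9 and the synopsis stop wording must also be reconciled, since exactly seven successes satisfies both go and stop.

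The cost is protocol wording and one additional line in the Part 1 report, with no extra patients or procedures. The downside is that the stated feasibility may look less favourable.

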## 4 METHODOLOGY

### 4.1 Study Design

This is an open-label, non-randomized, single center, study of IVM observation in conjunction with fluorescein in subjects with deep space solid tumors undergoing surgical resection. The first part is a Pilot study of feasibility.

Subjects will be treated on an inpatient basis. All subjects will meet the inclusion and exclusion criteria summarized in **Section 5.1** and **Section 5.2** prior to participation in this study. Standard evaluation by the Preoperative Anesthesia clinic may include additional testing such as EKG, chest x-ray, and/or pulmonary function tests, but this is performed based upon their established

guidelines. If any of these tests preclude a surgery in the operating room, then the patient is excluded from this study.

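### Recorded video is read off-line with no masking of the reader to before/after status or tumor grade and no lock before linkage, so expectation could bias the grade and Aim 2 comparisons

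*Combined protocol and SAP*

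**What the plan says.** Section 4.1 describes the study as open-label and non-randomized. Section 4.2 sets out the reading: "Off-line analysis of digitally recorded live video will be performed", with methods taken from the group's preclinical imaging work. The measured quantities come from the same step: "Lumenal cross-sectional diameter (D) of vessels and velocity (V) of dye labeled cells will be measured in off-line observations". On automation it says only: "Software is available from Mauna Kea, which can analyze and calculate these data". It does not say that the software must be used or that its output is independent of the operator.

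Section 9 lists what makes an observation abnormal. Two of the five criteria are verbal. One is vessel structure (tortuosity or a closed loop). The other is branching: "Aberrant vessel branching patterns compared to normal tissue, which includes erratic and disorganized branching points". These normal/aberrant calls go to McNemar's test. Vessel density and average flow rate go to a paired t test. Similar analyses are planned for readings before versus after fluid bolus or vasopressor. The readings are also to be correlated with tumor grade and with survival.

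The one nearby safeguard, in section 4.2, is that "all data will be de-identified and provided to the Biostatistician". The protocol does not name the reader or the number of readers. It says nothing about masking, clip coding, reading order, or a lock of readings before grade or follow-up is attached.

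**The concern.** A reader who knows the answer hoped for can lean toward it when the reading involves judgment. Three features of the plan leave room for this.

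- **Judgment.** Structure and branching have no numerical threshold. The measured items also leave discretion, because no rule says which vessels, frames or cells within the 2-4 recorded areas are measured.
- **Knowledge of timing.** Aim 2 in the synopsis hopes to reproduce in patients the enhanced tumor flow seen in the group's animal models. Nothing stops the reader knowing which clip is the later one.
- **Knowledge of grade and outcome.** Final pathology arrives 5-7 days after surgery, and clinical follow-up is collected for up to 10 years and matched to the microscopy data. No reading deadline precedes either.

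At stake are the conclusions that Part II and Aim 2 are meant to deliver: whether tumor vessels differ by grade, and whether flow changes after the hemodynamic manipulation. An association produced by the reader would look the same in the results as a real one.

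**Working it through.** The plan states no significance level, power, effect size or reader agreement for these comparisons, so there is no figure of its own to reproduce. The check has two parts.

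**1. Who could know what, and when**

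| Information | When available | Barrier stated in the protocol |
|---|---|---|
| Before/after status | At recording (section 4.2) | None |
| Tumor grade | 5-7 days after surgery (sections 3.3 and 9) | None |
| Recurrence, death | Up to 10 years (section 6.3, notes to Study Calendar) | None |

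De-identification applies to data passed to the biostatistician. It comes after the reading and does not mask the person scoring the clip.

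**2. How much a reader shift could matter (illustration)**

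*Continuous before/after readings, paired t test.* Assume no true effect, a two-sided 5% test, and a reader who shifts one condition by b SDs of the paired differences. The test statistic is then non-central t with n − 1 degrees of freedom and non-centrality b√n. The probability of significance is P(|T| > t at 0.975, n − 1 df).

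The number of pairs is not stated. A second observation is made only when a bolus or vasopressor is required and given (section 4.2), so 50 is a ceiling; 20 and 30 are assumed lower values.

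Example: n = 20, b = 0.3 gives non-centrality 0.3 × √20 = 1.342, critical value 2.093, probability 0.247. For n = 50, b = 0.3: 0.3 × √50 = 2.121, critical value 2.010, probability 0.548.

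| Assumed shift (SD of paired differences) | n = 20 | n = 30 | n = 50 (ceiling) |
|---|---|---|---|
| 0 | 5% | 5% | 5% |
| 0.2 | 14% | 19% | 28% |
| 0.3 | 25% | 36% | 55% |
| 0.4 | 40% | 56% | 79% |

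*Structure and branching calls, exact McNemar.* Assume 30% truly aberrant in both conditions, independently, and that the reader upgrades 20% of normal readings in the expected condition only. The aberrant rate there becomes 0.30 + 0.70 × 0.20 = 0.44. The discordant probabilities are 0.44 × 0.70 = 0.308 and 0.56 × 0.30 = 0.168. Enumerating the binomial gives significance 8% of the time at n = 20 and 23% at n = 50, against 2% and 3% with no upgrading.

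*Grade.* No test is named. For scale only, assume 25 versus 25 patients, a two-sided 5% comparison of means by normal approximation, and a 0.3 SD shift (here the SD of the reading itself). The standardized difference is 0.3 / √(2/25) = 1.061, giving 19%.

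Survival is planned by Kaplan-Meier, and none of these figures applies to it.

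**The case against.** Several points on the other side stand.

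- **Recoverability.** A reader might infer that unmasked reading would spoil the data for good. The documents do not support that: section 4.2 keeps the raw video available for review, so a masked re-read is possible later.
- **Scope of the figures.** It is tempting to take the n = 50 paired t results as the size of the problem everywhere. They apply only to the continuous before/after readings, and 50 pairs is a ceiling. The paired t test is reserved for density and flow rate, which are measured and may be helped by software; the most subjective items go to McNemar.
- **Survival.** This route is weak if clips are read promptly. Part I readings must be done early to decide feasibility, and section 11.1 asks for database entry within about 28 days of the visit, with an audit trail. That is only a partial safeguard, because the readings are kept in a spreadsheet that the protocol does not say is entered in that database.
- **Primary endpoint.** A reader might extend the concern to feasibility. Success in sections 3.3 and 9 depends on whether the parameters could be measured, not on their values.
- **Limits of masking.** After-clips follow a second fluorescein dose in the same operation, and residual dye could reveal them. Tumor versus normal tissue may be obvious on video. Masking does not touch the choice of areas imaged in surgery.

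What these points leave untouched is that the reader is not masked to timing or grade and that no lock precedes linkage.

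**Conclusion.** The concern holds as a risk of bias, not as evidence that bias has occurred. It bears mainly on the secondary grade comparison and the Aim 2 before/after comparison, and less on survival, where it matters only if clips are read or re-read late.

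On size, a modest assumed shift of 0.3 SD would take the paired t test from 5% to 25% false positives with 20 pairs. The McNemar and grade illustrations point the same way. The size of the shift, the number of pairs, the 5% level, the aberrant rate and the grade split are all assumptions; the documents anchor none of them.

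The change is worth making because the video is already recorded and read off-line, so the safeguard is cheap and feasible.

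**What to change.** Add to section 4.2:

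1. The coordinator gives each clip a random code and holds the key.
2. The existing reader scores clips in random order, without access to before/after status, grade or follow-up.
3. Scores are locked before grade or follow-up is linked.
4. Any later re-read is done masked and reported separately from the locked scores.

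The cost is a small amount of coding work and one lock step by existing staff. No extra reader, patient or visit is needed, and the sample size does not change. The report should state that before/after masking may be incomplete if residual dye is visible, that tumor versus normal tissue may not be maskable, and that the choice of areas imaged during surgery is not addressed.

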### 3.3 PRIMARY AND SECONDARY ENDPOINTS:

*Primary endpoint:* A patient will be deemed a success if each of the following parameters were measured:

1. Identify tumor associated vessels and measure vessel diameters
2. Determine vessel density per 10x field
3. Visualize vital dyes within the tumor-associated vessels (fluorescein)
4. Calculate the blood flow velocity of the tumor-associated vessels and tissue penetration of fluorescein as a marker of vessel permeability.

Measurements will be obtained before and after any tumor vessel manipulation with either bolus fluids or vasopressors.

*Secondary endpoints:*

1. Post-operative comparison of the microvasculature of tumor with normal tissue (e.g. peritoneum) in each individual subject using vessel diameters, vessel density, detection of intravital dye and flow rates.
2. Post-operative correlation of the microvasculature with pathologic features of the tumor (i.e. tumor grade) at the time of the final pathology report (5-7 days after surgery).
3. Post-operative correlation of the microscopic observation of the tumor microvasculature tumor-specific and overall survival.

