A matched analysis will be performed for observations of microvasculature between the tumor and normal tissue. For dichotomous variable comparisons between vessel structure (normal vs aberrant), vessel branching patterns (normal vs aberrant), or detection of intravital dye (present vs absent), a McNemar's test will be performed. For continuous variable comparisons between blood vessel density and average blood flow rate, a paired t test will be performed.

Associations between characteristics for the baseline (normal peritoneal microvasculature observed surrounding the tumor) and tumor itself will be depicted with graphics, correlations, and model results.

Similar analyses will be performed to compare baseline observations with those performed after fluid bolus and/or vasopressor administration.

Adverse event and complication rates will be described using upper one-sided 95% Clopper Pearson confidence limits.

Overall survival will be defined as the duration of time from diagnosis to time of death. Disease specific survival will be defined as the time from surgery to death due to recurrence. Overall survival and disease specific survival will be generated using standard Kaplan-Meier methodology.

A maximum of 50 subjects will be enrolled in this study (initially 10 to determine feasibility and then 40 additional subjects if deemed feasible). The accrual rate is estimated at 1-2 subjects per month, and the estimated study duration is 30 months (2.5 years).

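### The only flow equation is labelled a velocity but does not yield one, and the flow analyses never name the variable they use

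*Combined protocol and SAP*

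**What the plan says.** Section 4.2 describes the off-line measurements: "Lumenal cross-sectional diameter (D) of vessels and velocity (V) of dye labeled cells will be measured in off-line observations". Wall shear rate is computed from these as 8(V/D). Then comes the one flow formula, introduced by "Blood flow velocity will be determined by the equation" and printed as "Q = (RBC \text{ velocity}/1.6) \times (d/2) \times \pi". No units are given. The section adds that vendor software can calculate these data, without naming a flow variable.

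Two different terms are used afterwards:

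- Section 3.3, success criterion 4: "Calculate the blood flow velocity of the tumor-associated vessels and tissue penetration of fluorescein as a marker of vessel permeability".
- Section 3.3, secondary endpoint 1, compares tumor with normal tissue "using vessel diameters, vessel density, detection of intravital dye and flow rates".
- Section 9, abnormality criterion 5: "Average blood flow rate through observed vessel that is less than one standard deviation of the average blood flow rate through a normal vessel".
- Section 9, matched analysis: "For continuous variable comparisons between blood vessel density and average blood flow rate, a paired t test will be performed".
- Section 9, Aim 2 comparison: "Similar analyses will be performed to compare baseline observations with those performed after fluid bolus and/or vasopressor administration".

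**The concern.** A velocity is a length per unit time. An equation that multiplies a velocity by a length, or by an area, returns something else. The label in Section 4.2 therefore does not match what is computed, and this equation is the only definition of flow in the plan.

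The mismatch carries into the analyses. Someone programming the paired t test on *average blood flow rate* could use the measured cell velocity V, the scaled velocity V/1.6, or Q, and could point to Section 4.2 for any of them. These quantities need not agree in direction. Aim 2 asks whether tumor blood flow is enhanced after a fluid bolus or vasopressor. Faster flow through a narrower vessel could be reported as a rise on velocity and a fall on volume. Leaving the variable unnamed also leaves the choice open until after the data have been seen.

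**Working it through.** **Inputs.** The label, the equation, D (a length) and V (length/time) come from Section 4.2. The terms used in the analyses come from Sections 3.3 and 9. The documents give no tumor/normal ratio of diameter or velocity and no numerical flow value, so there is no stated figure to reproduce. All ratios and values below are assumptions for illustration.

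**Step 1: units.** Write L for length and T for time.

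- Velocity (V, or V/1.6): L/T.
- Q as printed: (L/T) × L = L²/T.
- Q with (d/2) squared: (L/T) × L² = L³/T.

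For example, take V = 500 µm/s and d = 10 µm. Then V/1.6 = 312.5 µm/s. Printed Q = 312.5 × 5 × π ≈ 4,909 µm²/s. Squared Q = 312.5 × 25 × π ≈ 24,544 µm³/s. Only the first is a velocity. The squared form is a scaled velocity times lumen area, which is a volumetric flow rate.

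**Step 2: which variable each analysis uses.**

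| Place | Term used | Tied to Q or V? |
|---|---|---|
| Section 4.2, equation | blood flow velocity | Q, but Q is not a velocity |
| Section 3.3, success criterion 4 | blood flow velocity | only through the label in 4.2 |
| Section 3.3, secondary endpoint 1 | flow rates | no |
| Section 9, abnormality criterion 5 | average blood flow rate | no |
| Section 9, paired t test | average blood flow rate | no |
| Section 9, before/after comparison | inherited from the above | no |

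**Step 3: does the choice matter?** For one pair of vessels, let r be the diameter ratio and v the velocity ratio (tumor/normal, or after/before). The constants 1.6, 2 and π cancel.

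- Ratio on velocity = v.
- Ratio on volumetric flow = v × r².

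With r = 1.5 and v = 0.8, velocity gives 0.8 and volumetric flow gives 0.8 × 2.25 = 1.8. The first says lower flow in tumor and the second says higher.

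The two disagree in direction when v lies between 1/r² and 1:

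| Assumed diameter ratio r | Velocity ratios v for which the directions differ |
|---|---|
| 0.8 | 1.0 to 1.56 |
| 1.0 | none; both equal v |
| 1.25 | 0.64 to 1.0 |
| 1.5 | 0.44 to 1.0 |
| 2 | 0.25 to 1.0 |

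Disagreement therefore requires velocity and diameter to move in opposite directions, within a bounded range. The printed form without the square would give v × r = 1.2 in the example. That figure matters only if the source document really lacks the exponent.

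**The case against.** The strongest reply is that the intent is easy to infer. The symbol Q, the divisor 1.6 and the factor π(d/2) all point to volumetric flow. V is listed separately and used for shear rate. Flow rate through a vessel most naturally means Q. This is fair, and Q is probably what was meant. But the reader then has to set aside the printed label, and Section 9 never states the link. Section 4.2 also refers to methods from the group's preclinical work and to vendor software. The definition may be settled there, but those sources are not part of the plan.

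A second reply is that the illustration is one vessel pair with assumed ratios, whereas the paired t test uses patient-level averages from 2 to 4 areas of each tissue. This stands. The working shows that the direction can differ, not that it will.

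Four stronger readings are tempting and are not supported:

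- *The plan dropped the square from the formula.* A superscript is easily lost when a PDF is converted to text, so this cannot be asserted without the source page. The wrong label does not depend on it.
- *Criterion 5 classifications would reverse.* That criterion turns on a one-standard-deviation threshold, and the documents give no standard deviation, so no effect can be computed. It is also one of five alternative criteria.
- *The feasibility result is undermined.* Success requires only that the parameters were measured, and criterion 1 already requires diameters.
- *RBC velocity and V are different measurements.* Section 4.2 describes one cell velocity. Reading the two as the same is straightforward, and this is at most a matter of wording.

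**Conclusion.** The label is wrong under either reading of the equation. This follows from units alone and needs no assumption. It is equally clear that the protocol text does not say which quantity enters the flow analyses, although Q is the natural reading.

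The consequence is conditional. Where velocity and diameter change in opposite directions, velocity and volumetric flow can give opposite answers (0.8 against 1.8 in the assumed example). Where diameters are equal, they agree. The analyses exposed are the secondary tumor-versus-normal comparison and the before/after comparison, the latter only in patients who receive a bolus or vasopressor. The effect on criterion 5 is unquantified, and the Part I decision is essentially unaffected. The point should be fixed before the secondary analyses are run; it does not threaten the study's go/no-go rule.

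**What to change.** 1. Check the source document for an exponent on (d/2).
2. Restate the sentence in Section 4.2 as: volumetric blood flow rate Q = (RBC velocity/1.6) × π × (d/2)², in length³/time. If the source already carries the square, only the label changes.
3. Define blood flow velocity separately, in length/time: the measured V, or V/1.6 if mean velocity is meant.
4. In Section 9, name the variable used in criterion 5, in the paired t test and in the before/after comparison.
5. Success criterion 4 may keep velocity and secondary endpoint 1 may keep flow rate, provided each is defined. There is no need to force one term on both.
6. Confirm that the vendor software uses the same formula. The wall shear rate formula needs no change.
7. Recalculate any existing values. Where an unsquared Q was stored vessel by vessel with its diameter, volumetric flow is that value times d/2, and V/1.6 is that value divided by (π × d/2). Patient averages alone would not be enough, because an average of products is not the product of averages.

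The cost is a few lines of text and some recalculation. Section 4.2 says that generated data and raw video are kept, so values can be recomputed or re-measured without new patient contact.
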